**8.3 Collection of adverse events**

The Principal Investigator is responsible for ensuring that all staff involved in the study are familiar with the content of this section.

The definitions of an AE or SAE can be found in [Appendix B](#).

AE will be reported by the subject (or, when appropriate, by a caregiver, surrogate, or the subject's legally authorized representative).

The investigator and any designees are responsible for detecting, documenting, and recording events that meet the definition of an AE or SAE. For information on how to follow/up AEs see section 8.3.3.

**8.3.1 Method of detecting AEs and SAEs**

Care will be taken not to introduce bias when detecting AEs and/or SAEs. Open-ended and non-leading verbal questioning of the subject is the preferred method to inquire about AE occurrences.

**8.3.2 Time period and frequency for collecting AE and SAE information**

Adverse Events (new and ongoing from predecessor study) will be collected from time of signature of consent form throughout the treatment period and including the follow-up CCI CCI period.

Tezepelumab - D5180C00018

All SAEs will be recorded and reported to the sponsor or designee within 24 hours, as indicated in [Appendix B](#). The investigator will submit any updated SAE data to the sponsor within 24 hours of it being available.

Investigators are not obligated to actively seek AE or SAE in former study subjects. However, if the investigator learns of any SAE, including a death, at any time after a subject's last visit and he/she considers the event to be reasonably related to the study treatment or study participation, the investigator may notify the sponsor.

The method of recording, evaluating, and assessing causality of AE and SAE and the procedures for completing and transmitting SAE reports are provided in [Appendix B](#).

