## 8.4 Safety reporting and medical management

### 8.4.1 Reporting of serious adverse events

All SAEs have to be reported, whether or not considered causally related to the investigational product, or to the study procedure(s). All SAEs will be recorded in the CRF.

Tezepelumab - D5180C00018

If any SAE occurs in the course of the study, then Investigators or other site personnel inform the appropriate AstraZeneca representatives within one day i.e., immediately but **no later than 24 hours** of when he or she becomes aware of it.

The designated AstraZeneca representative works with the Investigator to ensure that all the necessary information is provided to the AstraZeneca Subject Safety data entry site **within 1 calendar day** of initial receipt for fatal and life-threatening events **and within 5 calendar days** of initial receipt for all other SAEs.

For fatal or life-threatening adverse events where important or relevant information is missing, active follow-up is undertaken immediately. Investigators or other site personnel inform AstraZeneca representatives of any follow-up information on a previously reported SAE within one calendar day i.e., immediately but **no later than 24 hours** of when he or she becomes aware of it.

Once the Investigators or other site personnel indicate an AE is serious in the WBDC system, an automated email alert is sent to the designated AstraZeneca representative(s).

If the WBDC system is not available, then the Investigator or other study site staff reports a SAE to the appropriate AstraZeneca representative by telephone.

The AstraZeneca representative(s) will advise the Investigator/study site staff how to proceed.

For further guidance on the definition of a SAE, see Appendix B of the Clinical Study Protocol.

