#### **Regulatory Reporting Requirements for SAEs**

- Prompt notification by the investigator to the sponsor of an SAE is essential so that legal obligations and ethical responsibilities towards the safety of participants and the safety of a study intervention under clinical investigation are met.
- The sponsor has a legal responsibility to notify both the local regulatory authority and other regulatory agencies about the safety of a study intervention under clinical investigation. The sponsor will comply with country-specific regulatory requirements relating to safety reporting to the regulatory authority, Institutional Review Boards (IRB)/Independent Ethics Committees (IEC), and investigators.
- For all studies except those utilizing medical devices investigator safety reports must be prepared for suspected unexpected serious adverse reactions (SUSARs) according to local regulatory requirements and sponsor policy and forwarded to investigators as necessary.
- An investigator who receives an investigator safety report describing an SAE or other specific safety information (eg, summary or listing of SAEs) from the sponsor will

Tezepelumab - D5180C00018

review and then file it along with the [Investigator's Brochure or state other documents] and will notify the IRB/IEC, if appropriate according to local requirements.

The investigator will be responsible for the following:

- Providing written summaries of the status of the study to the IRB/IEC annually or more frequently in accordance with the requirements, policies, and procedures established by the IRB/IEC
- Notifying the IRB/IEC of SAEs or other significant safety findings as required by IRB/IEC procedures
- Providing oversight of the conduct of the study at the site and adherence to requirements of 21 CFR, ICH guidelines, the IRB/IEC, European regulation 536/2014 for clinical studies (if applicable), and all other applicable local regulations

The study will be performed in accordance with the AstraZeneca policy on Bioethics and Human Biological Samples.

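### Protocol 8.3.2 leaves it optional to report a related SAE or death learned of after a subject's last visit; notification should be mandatory

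*Protocol*

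**What the plan says.** Section 8.3.2 of the protocol contains two rules of different strength.

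- For the collection period, which runs from consent through treatment and follow-up, the rule is firm: "All SAEs will be recorded and reported to the sponsor or designee within 24 hours".
- For former subjects, it first removes any duty to search: "Investigators are not obligated to actively seek AE or SAE in former study subjects". It then turns to an event that reaches the investigator unprompted: "if the investigator learns of any SAE, including a death, at any time after a subject's last visit". If the investigator also judges that event related to study treatment or to taking part, "the investigator may notify the sponsor".

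Two other places bear on the point. Section 8.4.1 states that "All SAEs have to be reported, whether or not considered causally related to the investigational product". Appendix A 1, under the regulatory reporting requirements for SAEs, states that "Prompt notification by the investigator to the sponsor of an SAE is essential", and gives legal obligations and participant safety as the reason.

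**The concern.** The permissive verb applies to a narrow but valuable class of case: a serious event, possibly fatal, that the investigator already knows about and already suspects is related. Nobody has to look for it, and all that remains is to pass it on.

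This is the long-term safety study of an antibody acting on an upstream immune pathway. Its adverse events of special interest (protocol 8.3.8) include malignancy and opportunistic infection, which can plausibly come to light late. Other subjects may still be dosed or followed when such a case arises. The sponsor prepares safety reports on suspected unexpected serious reactions (Appendix A 1) and keeps the right to break the code for them (protocol 6.3). The safety monitoring board reviews cumulative data (8.4.6). None of them can act on a case the sponsor has not been told about.

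**Working it through.** The plan gives no figure on this point, so the check is a comparison of sections, asking of each whether it obliges the investigator to report a related SAE first learned of after the last visit.

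1. **Protocol 8.3.2.** Mandatory within 24 hours during the collection period, optional afterwards. The change of verb within one section is explicit.
2. **Protocol 8.4.1.** Its opening sentence is broad, but the 24-hour duty is introduced for an SAE that occurs during the study. The clock starts when the investigator becomes aware, with no cut-off at the last visit. An SAE with onset in the study but discovered later is therefore arguably still mandatory here, although 8.3.2, which is worded by when the event is learned of, appears to make it optional. An SAE with onset after exit is not expressly reached.
3. **Appendix B 2.** The SAE definition is tied to study phases, so it adds no duty after exit.
4. **Protocol 8.3.3.** Follow-up beyond the last assessment concerns events already unresolved at that point. It does not cover new ones.
5. **Appendix A 1.** It calls prompt notification essential and sets no time limit, but it states a principle and does not address former subjects.
6. **Protocol 8.4.2.1 and 8.4.2.2.** Pregnancy outcomes must be followed and documented even after a subject has been discontinued from the study. For partners, this covers conceptions up to 16 weeks after the last dose. So the protocol does impose firm duties beyond participation where it chooses to.

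No visible section makes notification mandatory for a related SAE with onset after exit.

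**When the gap opens.** The last dose is at Week 100 and the second follow-up visit at Week 116, so a subject completing that schedule is covered for 116 − 100 = 16 weeks. The protocol equates 16 weeks with five half-lives (5.3, 8.4.2.2). A subject who withdraws from the study *w* weeks after the last dose, with *w* below 16, leaves 16 − *w* weeks of that span under the permissive rule. As an illustration, *w* = 4 leaves 12 weeks and *w* = 8 leaves 8. The documents do not say how many subjects would withdraw in this window.

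**Whether planned results are affected.** The primary objective uses on-treatment events (protocol 9.4.2), and the SAP closes even the wider on-study window at completion or withdrawal (SAP 3.2.2). An SAE with onset after exit would enter no planned rate, reported or not.

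**The case against.** The best defence is that the protocol is coherent as it stands: mandatory reporting covers the study phases and 8.3.2 governs what follows. Collection for subjects completing the Week 116 schedule already extends to five half-lives. Subjects who only stop treatment are still offered a visit 16 weeks after the last dose and contact at Week 104 (7.1.1). Nothing discourages a site from reporting. Much of this stands, and it rules out four stronger readings that a reader might infer.

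- *The protocol contradicts itself.* It does not. Appendix A 1 is a general principle, and the 24-hour rule in 8.4.1 is limited to events in the course of the study.
- *A site that stays silent about a related late death is compliant.* That follows from the one sentence in 8.3.2 taken alone. Appendix A 1 also binds sites to good clinical practice, to applicable law and to the ethics committee's own procedures for safety findings. What those require cannot be seen here, so neither compliance nor breach can be asserted.
- *The gap applies to all of about 975 planned subjects from Week 116.* Table 1 and SAP 3.1.5.1 show that some subjects enter a further period, redacted in these copies, so their last visit is not Week 116.
- *Related cases are lost from the safety analysis.* Permission is not suppression, and the planned rates do not use events with onset after exit.

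What the defence does not answer is why a known, serious and suspected-related event should be left to discretion at all.

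**Conclusion.** The concern holds in a limited form. Protocol 8.3.2 makes notification optional for a related SAE or death learned of after the last visit, and no visible section overrides it. The clear gap is new onset after study exit, and it matters most for early withdrawals within 16 weeks of the last dose. For in-study events discovered late, the problem is one of clarity, because 8.3.2 and 8.4.1 can be read differently.

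The consequence falls on sponsor surveillance and expedited reporting. Its size cannot be quantified: the documents give no rate of late related SAEs, no visible withdrawal rate, and nothing on how often sites would report voluntarily. The conclusion rests on the visible text and on reading the verb in its ordinary permissive sense. This is a worthwhile and inexpensive improvement to the protocol, not a defect in the trial's analysis.

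**What to change.** In protocol 8.3.2:

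- Replace the permissive clause so that the investigator must promptly notify the sponsor, on the 8.4.1 timelines.
- Add a sentence stating that an SAE with onset during the study but discovered after the last visit remains reportable under 8.4.1.
- Keep the sentence that investigators need not actively look for events in former subjects.

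No visit, data collection or analysis is added, and the SAP needs no change.

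The cost is more than the edit itself. A protocol amendment needs ethics committee approval before implementation (Appendix A 1), a letter has to go to about 350 sites (protocol 4.1), and a few extra case reports would need processing. Bundling the change with another amendment would absorb most of this.

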### **8.3.3 Follow-up of AEs and SAEs**

After the initial AE/SAE report, the investigator is required to proactively follow each subject at subsequent visits/contacts. All SAE/non-serious AEs/AEs of special interest will be followed until resolution, stabilization, the event is otherwise explained, or the subject is lost to follow-up.

Any AEs that are unresolved at the subject's last AE assessment or other assessment/visit as appropriate in the study are followed up by the Investigator for as long as medically indicated, but without further recording in the CRF. AstraZeneca retains the right to request additional information for any subject with ongoing AE(s)/SAE(s) at the end of the study, if judged necessary.

### **8.3.4 Adverse event data collection**

The following variables will be collected for each AE:

- AE (verbatim)
- The date when the AE started and stopped
- Whether the AE is serious or not
- Investigator causality rating against the Investigational Product(s) (yes or no)
- Action taken with regard to Investigational Product(s)
- AE intensity (mild, moderate, severe)
- Outcome.

In addition, the following variables will be collected for SAEs:

- Date AE met criteria for serious AE

Tezepelumab - D5180C00018

- Date Investigator became aware of serious AE
- AE is serious due to
- Date of hospitalisation
- Date of discharge
- Probable cause of death
- Date of death
- Autopsy performed
- Causality assessment in relation to Study procedure(s)
- Causality assessment to other medication(s)

### 8.3.5 Causality collection

The Investigator will assess causal relationship between Investigational Product and each Adverse Event, and answer 'yes' or 'no' to the question 'Do you consider that there is a reasonable possibility that the event may have been caused by the investigational product?'

For SAEs, causal relationship will also be assessed for other medication and study procedures. Note that for SAEs that could be associated with any study procedure the causal relationship is implied as 'yes'.

A guide to the interpretation of the causality question is found in Appendix B to the Clinical Study Protocol.

### 8.3.6 Adverse events based on signs and symptoms

All AEs spontaneously reported by the subject or care provider or reported in response to the open question from the study site staff: *'Have you/the child had any health problems since the previous visit/you were last asked?'* or revealed by observation will be collected and recorded in the CRF. When collecting AEs, the recording of diagnoses is preferred (when possible) to recording a list of signs and symptoms. However, if a diagnosis is known and there are other signs or symptoms that are not generally part of the diagnosis, the diagnosis and each sign or symptom will be recorded separately.

### 8.3.7 Adverse events based on examinations and tests

The results from the Clinical Study Protocol mandated laboratory tests and vital signs will be summarized in the CSR. Deterioration as compared to predecessor study baseline in protocol-mandated laboratory values and vital signs should therefore only be reported as AEs if they fulfil

Tezepelumab - D5180C00018

any of the SAE criteria or are the reason for premature discontinuation of treatment with the investigational product.

If deterioration in a laboratory value/vital sign is associated with clinical signs and symptoms, the sign or symptom will be reported as an AE and the associated laboratory result/vital sign will be considered as additional information. Wherever possible the reporting Investigator uses the clinical, rather than the laboratory term (e.g. anaemia versus low haemoglobin value). In the absence of clinical signs or symptoms, clinically relevant deteriorations in non-mandated parameters should be reported as AE(s).

Any new or aggravated clinically relevant abnormal medical finding at a physical examination as compared with the baseline assessment will be reported as an AE unless unequivocally related to the disease under study, see sections [8.3.9](#) and [8.3.10](#).

When collecting AEs, the recording of diagnoses is preferred, when possible, to recording a list of signs and symptoms. Asthma symptoms or signs, such as wheeze, cough, chest tightness, dyspnea, breathlessness and phlegm, will be recorded as AEs only when:

- The sign or symptom is serious according to definitions, see [Appendix B](#)
- The subject prematurely discontinues IP due to the sign or symptom
- The sign or symptom is new to the subject or not consistent with the subject's preexisting asthma history (defined as within 1 year of Visit 1 in predecessor study), as judged by the Investigator.

Asthma exacerbation should be recorded as an AE or SAE only if it fulfills any of the above criteria.

### **8.3.8 Adverse Events of Special Interest**

An adverse event of special interest (AESI) is an event of scientific and medical interest towards improving the understanding of the IP. An AESI may be serious or non-serious. For this study, AESIs include:

1. Anaphylactic reactions
2. Immune complex disease (Type III hypersensitivity reactions)
3. Malignancy
4. Helminth infections
5. Severe infections which are defined as:

Tezepelumab - D5180C00018

- SAEs or
  - Requiring treatment with systemic antiviral medications, intravenous antibiotics or medications for helminth parasitic infection or
  - Requiring a premature and permanent discontinuation of study drug
6. Injection site reactions
  7. Opportunistic infections
  8. Guillain-Barre Syndrome
  9. Adrenal crisis

### 8.3.9 Hy's Law

Cases where a subject shows elevation in liver biochemistry may require further evaluation and occurrences of AST or ALT  $\geq 3 \times \text{ULN}$  together with total bilirubin  $\geq 2 \times \text{ULN}$  needs to be reported as SAEs. Please refer to [Appendix D](#) for further instruction on cases of increases in liver biochemistry and evaluation of Hy's Law.

### 8.3.10 Disease-under study (DUS)

Asthma symptoms or signs, such as, wheeze, cough, chest tightness, dyspnoea, breathlessness and phlegm, will be recorded as AEs when:

- the sign or symptom is serious according to definitions, see [Appendix B](#)
- the subject prematurely discontinues IP due to the sign or symptom, and/or
- the sign or symptom is new to the subject or not consistent with the subject's pre-existing asthma history as judged by the Investigator

Asthma exacerbations should not be recorded as AEs, unless it fulfils any of the above criteria.

All asthma exacerbations should be recorded in the EXACATE module as per Section [8.1.1](#).

## 8.4 Safety reporting and medical management

### 8.4.1 Reporting of serious adverse events

All SAEs have to be reported, whether or not considered causally related to the investigational product, or to the study procedure(s). All SAEs will be recorded in the CRF.

Tezepelumab - D5180C00018

If any SAE occurs in the course of the study, then Investigators or other site personnel inform the appropriate AstraZeneca representatives within one day i.e., immediately but **no later than 24 hours** of when he or she becomes aware of it.

The designated AstraZeneca representative works with the Investigator to ensure that all the necessary information is provided to the AstraZeneca Subject Safety data entry site **within 1 calendar day** of initial receipt for fatal and life-threatening events **and within 5 calendar days** of initial receipt for all other SAEs.

For fatal or life-threatening adverse events where important or relevant information is missing, active follow-up is undertaken immediately. Investigators or other site personnel inform AstraZeneca representatives of any follow-up information on a previously reported SAE within one calendar day i.e., immediately but **no later than 24 hours** of when he or she becomes aware of it.

Once the Investigators or other site personnel indicate an AE is serious in the WBDC system, an automated email alert is sent to the designated AstraZeneca representative(s).

If the WBDC system is not available, then the Investigator or other study site staff reports a SAE to the appropriate AstraZeneca representative by telephone.

The AstraZeneca representative(s) will advise the Investigator/study site staff how to proceed.

For further guidance on the definition of a SAE, see Appendix B of the Clinical Study Protocol.

#### **8.4.2 Pregnancy**

All pregnancies and outcomes of pregnancy should be reported to AstraZeneca.

If a pregnancy is reported, the investigator should inform the sponsor within 24 hours of learning of the pregnancy. Any cases of pregnancy during the treatment or follow-up CCI CCI period will be recorded in the specific eCRF module.

Abnormal pregnancy outcomes (e.g., spontaneous abortion, foetal death, stillbirth, congenital anomalies, ectopic pregnancy) are considered SAEs.

##### **8.4.2.1 Maternal exposure**

If a subject becomes pregnant during the course of the study, investigational product should be discontinued immediately.

Pregnancy itself is not regarded as an adverse event unless there is a suspicion that the investigational product under study may have interfered with the effectiveness of a contraceptive medication. Congenital anomalies/birth defects and spontaneous miscarriages should be reported and handled as SAEs. Elective abortions without complications should not be handled as AEs.

Tezepelumab - D5180C00018

The outcome of all pregnancies (spontaneous miscarriage, elective termination, ectopic pregnancy, normal birth or congenital anomalies) should be followed up and documented even if the subject was discontinued from the study.

If any pregnancy occurs in the course of the study, then the Investigator or other site personnel informs the appropriate AstraZeneca representatives within 1 day i.e., immediately but **no later than 24 hours** of when he or she becomes aware of it.

The designated AstraZeneca representative works with the Investigator to ensure that all relevant information is provided to the AstraZeneca Subject Safety data entry site within 1 or 5 calendar days for SAEs (see Section 8.4.1) and within 30 days for all other pregnancies.

The same timelines apply when outcome information is available.

The PREGREP module in the CRF is used to report the pregnancy and the PREGOUT is used to report the outcome of the pregnancy.

#### 8.4.2.2 Paternal exposure

Pregnancy of the subject's partners will not be considered an AE. However, the outcome of all pregnancies (spontaneous miscarriage, elective termination, ectopic pregnancy, normal birth, or congenital anomaly) should be followed up and documented in the pregnancy report form for conceptions occurring from the date of the first administration of IP until 16 weeks (5 half-lives) after the last administration of IP. Consent from the partner must be obtained before the pregnancy report form is completed.

